11.3 Minimization of Anticipated Risks

Risks associated with the N-SWEAT Patch are minimized by design and training. Risks are minimized under this protocol due to:

- Only operators with proper training and experience will use the device
- Clinician users will be given the opportunity to use their discretion and medical expertise throughout the treatment and appropriately respond to the patient's reaction to treatment
- Only certified personnel will dispose of the device
- Extensive non-clinical evaluation of the device (animal and bench top testing)
- The use of standard medical grade materials in the manufacture of the device

CANDESANT BIOMEDICAL	CLINICAL STUDY PROTOCOL SAHARA STUDY	Document #: CB-CLP-001 Revision: E
-------------------------	---	---------------------------------------

11.4 Protocol Compliance

As with any clinical investigation, it is critical to conduct the study per the study protocol so as to not compromise the study results. Areas of particular criticality are as follows:

- Eligibility criteria (all treated subjects must be eligible per the protocol)
- Compliance with the protocol follow-up activity including patient reported outcomes and quality of life assessments
- Thorough, accurate, and timely reporting of AEs
- Thorough, accurate, and timely reporting of all clinical trial data

11.5 Safety-Related Stopping Rules

The study sponsor will be charged with monitoring the study for safety and for auditing the quality of the data. Stopping rules will be activated if there are any perceived safety concerns related to the N-SWEAT Patch as demonstrated by the occurrence of any of the following:

FIRST 10 SUBJECTS

1. One report of a Serious Adverse Event due to:
 - thermal or caustic injury
 - blister
 - erosion
 - pustule
 - erythema lasting > 7 days or developing >7 days after the treatment
 - infection
 - suspected infection of the skin or soft tissue in the axilla

AFTER 10 SUBJECTS

1. If 10% of N-SWEAT treated subjects have a reported severe device-related Adverse Event as defined in Table 6, or
2. If the DSMB recommends stopping due to a safety signal as described in section 10.4.

Should a stopping rule be triggered:

1. Enrollment and treatment will be suspended and a root cause investigation into all involved AEs will be conducted within 5 days by an independent Data Safety Monitoring Board to determine the cause of the event(s), to look at any trends and to evaluate potential safety issues.

CANDESANT BIOMEDICAL	CLINICAL STUDY PROTOCOL SAHARA STUDY	Document #: CB-CLP-001 Revision: E
---------------------------------	---	---------------------------------------

2. A full report (including photos, description, onset, duration, severity, causality, intervention, and sequalae) will be sent to FDA no later than 5 working days after DSMB review is complete.
3. Candesant will work with FDA, DSMB and study investigators to establish a process to re-start the study.

CANDESANT BIOMEDICAL	CLINICAL STUDY PROTOCOL SAHARA STUDY	Document #: CB-CLP-001 Revision: E
-------------------------	---	---------------------------------------

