5. STUDY OBJECTIVE

The primary objective of this study is to evaluate the safety and effectiveness of the N-SWEAT Patch in subjects who experience excessive sweating. The study is designed to confirm device safety shown in previous clinical studies and to demonstrate that the cohort of subjects treated with the N-SWEAT Patch will experience a reduction in sweating relative to sham treated controls.

The study will begin with a roll-in cohort of 10 subjects treated with the N-SWEAT device at one study site. After enrollment into this cohort is complete, adverse event data will be compiled and analyzed. Enrollment into the randomized cohort will commence after these safety data have been reviewed.

This prospective, multi-center, controlled, randomized, blinded, pivotal clinical study is intended to demonstrate sufficient safety and effectiveness of the N-SWEAT Patch for use in subjects with excessive sweating in order to obtain regulatory approval for marketing in the United States and certain other jurisdictions.

CANDESANT BIOMEDICAL	CLINICAL STUDY PROTOCOL SAHARA STUDY	Document #: CB-CLP-001 Revision: E
-------------------------	---	---------------------------------------

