9.6 Timing of Analyses

Safety for the Roll-in cohort will be summarized when at least 2 weeks of follow-up is available on the last enrolled roll-in subject.

Once all subjects complete 4 weeks of follow-up, the data will be summarized for evaluation of the endpoints. Lastly, the data will be summarized when all subjects complete 12 weeks of follow-up.

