10.1.3 Serious Adverse Events

A Serious Adverse Event (SAE) is an AE that:

- Led to death.
- Led to serious deterioration in the health of the participant, that either resulted in:
 - A life-threatening illness or injury. The term *life-threatening* in the definition of *serious* refers to an event in which the participant was at risk of death at the time of the event. It does not refer to an event that hypothetically might have caused death if it were more severe.
 - A permanent impairment of a body structure or a body function

CANDESANT BIOMEDICAL	CLINICAL STUDY PROTOCOL SAHARA STUDY	Document #: CB-CLP-001 Revision: E
-------------------------	---	---------------------------------------

- Inpatient or prolonged hospitalization. Planned hospitalization for a pre-existing condition, or a procedure required by the protocol, without serious deterioration in health, is not considered an SAE.
- Medical or surgical intervention to prevent life-threatening illness or injury or permanent impairment to a body structure or a body function.
- Led to fetal distress, fetal death, or a congenital abnormality or birth defect.

If an event is not an AE per the definition above, then it cannot be an SAE even if serious conditions are met (e.g., hospitalization for signs/symptoms of the disease under study, death due to progression of disease).

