10.2.1 Severity

The investigator will use the terms below to rate the severity of each AE.

Note that an event is defined as serious when it meets at least one of the predefined outcomes as described in the definition of an SAE, NOT when it is rated as severe per the table below.

Table 6. AE Severity

Severity	Description
Mild	Awareness of signs or symptoms, but easily tolerated and are of minor irritant type causing no loss of time from normal activities. Symptoms do not require therapy or a medical evaluation; signs and symptoms are transient.
Moderate	Events introduce a low level of inconvenience or concern to the participant and may interfere with daily activities, but are usually improved by simple therapeutic measures; moderate experiences may cause some interference with functioning
Severe*	Events interrupt the participant's normal daily activities and generally require systemic drug therapy or other treatment; they are usually incapacitating

Based on the National Institute on Aging (NIA) Adverse Event and Serious Adverse Event Guidelines (2018)

**Severe does not indicate an SAE (Serious Adverse Event). Please see 10.1.3 for a definition of Serious Adverse Event.*

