10.4 Independent Adverse Event Review

An independent Data Safety Monitoring Board (DSMB) will be established to protect patient safety and ensure data integrity for the Sahara Study. The board will be comprised of 3-5 clinical physicians with expertise in dermatology who are not participants in the study. The DSMB will serve in three roles in the safety overview of the Sahara study:

- To convene as needed for review of Adverse Events related to stopping rules and to determine a root cause analysis of these events.
- To conduct a monthly blinded review of all AEs reported during enrollment and until the final subject has reported for 4-week follow-up.
- If warranted, to request unblinding and fully investigate any potential safety signal. This investigation may result in a recommendation to stop the clinical study if the findings indicate an unacceptable or unknown safety risk.

A charter will establish the DSMB details on the operation of the DSMB.

CANDESANT BIOMEDICAL	CLINICAL STUDY PROTOCOL SAHARA STUDY	Document #: CB-CLP-001 Revision: E
-------------------------	---	---------------------------------------

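### In the first 10 subjects only a Serious Adverse Event stops the study automatically; a severe but non-serious device-related event does not

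*Protocol*

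**What the plan says.** Protocol section 11.5 has two lists. For the first 10 subjects there is a single item: "One report of a Serious Adverse Event due to" thermal or caustic injury, blister, erosion, pustule, prolonged or late erythema, or proven or suspected infection. After 10 subjects there are two items: "If 10% of N-SWEAT treated subjects have a reported severe device-related Adverse Event as defined in Table 6", and "If the DSMB recommends stopping due to a safety signal as described in section 10.4". When any item occurs, enrollment and treatment are suspended and the DSMB carries out a root-cause investigation within 5 days.

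Serious is defined by outcome in section 10.1.3. Short of death or fetal harm, the event must be one that "Led to serious deterioration in the health of the participant, that either resulted in" a life-threatening condition, permanent impairment, hospitalization, or an intervention to prevent such harm. Section 10.2.1 says an event is serious when it meets one of those outcomes, "NOT when it is rated as severe per the table below". Table 6 describes a severe event as one that interrupts daily life, generally needs systemic or other treatment and usually incapacitates.

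The roll-in cohort is 10 subjects at one site, all given N-SWEAT. Section 5 says of its review: "After enrollment into this cohort is complete, adverse event data will be compiled and analyzed". Section 9.6 summarizes roll-in safety "when at least 2 weeks of follow-up is available on the last enrolled roll-in subject". The SAP contains no stopping rule.

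**The concern.** The roll-in cohort exists to give a first safety assessment, yet its rule is narrower in kind than the one that follows it. The harms the protocol foresees are thermal and alkaline burns, blistering and skin erosion. A painful burn managed as an outpatient could be severe under Table 6 without meeting any outcome in section 10.1.3. Several listed causes (blister, pustule, erythema beyond 7 days) would not usually be serious on their own; that is a clinical judgment, not a figure in the documents. The early signal this device might plausibly give could therefore fall outside the roll-in rule. Whether the remaining roll-in subjects are treated before anyone examines the event would then rest on discretion.

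**Working it through.** The documents derive no operating characteristics for the stopping rules, so there is no planned figure to reproduce. The check compares the two lists and then sizes the gap under assumed rates.

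**The two lists side by side**

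| Event | First 10 subjects | After 10 subjects |
|---|---|---|
| SAE due to a listed cause | one event suspends | not listed |
| Severe, device-related, not serious | not listed | counts toward 10% |
| DSMB recommendation to stop | not listed | suspends |

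For a severe, non-serious device-related event, no number out of 10 reaches a first-10 trigger.

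**The later threshold on small denominators.** One event in k treated subjects is 1/k, which is at least 10% for every k up to 10. Had the 10% rule run from subject 1, a single event would have met it. Once the rule does apply, one event is not enough: 1/11 = 9.1%, so two are needed at 11 to 20 treated subjects and three at 30. The text does not say whether roll-in events carry forward. If they do, two severe roll-in events would start no pause in roll-in but would exceed the threshold at the 11th N-SWEAT subject (2/11 = 18.2%).

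**Chance that the gap is met.** With severe device-related rate p per subject, P(at least one in 10) = 1 − (1 − p)^10.

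| Assumed p | P(at least one in 10) |
|---|---|
| 1% | 9.6% |
| 2% | 18.3% |
| 5% | 40.1% |
| 10% | 65.1% |

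These are upper limits on the added chance of a pause, because some severe events would also be serious and already covered.

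**What earlier data exclude.** Protocol section 3.3 reports 12 + 8 = 20 N-SWEAT-treated subjects with three device-related events, two mild and one moderate, so 0 of 20 severe. The exact two-sided 95% upper limit is 1 − 0.025^(1/20) = 16.8%. All the assumed rates lie within it.

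**Exposure after a first event.** Suppose subjects are treated one at a time, the event is known at once and nobody uses discretion. Given at least one event, the mean number still to be treated is Σ(k = 1 to 10) p(1 − p)^(k−1)(10 − k) / [1 − (1 − p)^10].

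| Assumed p | Mean, given an event | Unconditional mean (× chance above) |
|---|---|---|
| 2% | 4.67 | 0.183 × 4.67 = 0.9 |
| 5% | 4.92 | 0.401 × 4.92 = 2.0 |
| 10% | 5.35 | 0.651 × 5.35 = 3.5 |

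**Pace.** The synopsis plans 10 roll-in subjects in 1.5 months: 10/1.5 = 6.7 per month, so about 7 are treated between monthly DSMB reviews.

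**The case against.** The strongest reply is that other safeguards cover roll-in.

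- One site treats all 10 subjects, so one team sees every reaction.
- Section 8.8 requires a 24-hour call, a 48–72-hour clinic visit, assessment within 24 hours of symptoms and an in-person visit for any suspected burn.
- Section 10.3 has moderate and severe AEs and all skin reactions reported to the sponsor within 5 working days.
- Section 10.4 gives the DSMB the task "To conduct a monthly blinded review of all AEs reported during enrollment" and lets it recommend stopping at any point.
- Section 15.1 lets the sponsor or investigator discontinue, and section 5 holds back randomization until roll-in safety has been reviewed.

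All of this is true and limits the consequence. None of it is an automatic suspension. As-needed DSMB meetings in section 10.4 are tied to events related to the stopping rules, so a severe, non-serious roll-in event does not clearly prompt one. The DSMB half of the fix does mainly formalize authority that already exists.

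Second, a one-event trigger is stricter in event count than the later rule: at a 5% rate, half the protocol's own threshold, it could pause roll-in up to 40.1% of the time. That stands as a real trade-off, though the result is a pause with an investigation and a restart process, not termination.

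Third, the 4.7 to 5.4 further subjects are conditional on an event and assume that nobody acts. The unconditional means are smaller. With reporting allowed up to 5 working days, about 1.5 subjects could still be treated in that week even under the fix (10 subjects over about 6.5 weeks). Some severe burns would also qualify as serious because of the intervention they need; the documents do not allow that overlap to be sized.

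**Conclusion.** The concern holds on the text. For severe, non-serious device-related events the rule is laxer in the first 10 subjects than afterward, and nothing in the SAP changes that. The size depends on an unknown rate: a 9.6% to 65.1% chance of at least one severe device-related event in roll-in for assumed rates of 1% to 10%, with serious events included in those figures. The population exposed is small, and the discretionary safeguards are substantial. This is a gap worth closing because closing it is cheap, not a defect that undermines the trial. Confidence is medium, mainly because the event rate and the overlap between severe and serious are not known.

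**What to change.** Leave the existing SAE trigger and its list of causes as they are. Under the first-10 heading in section 11.5 add two items:

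- *2. One report of a severe (Table 6) device-related Adverse Event, whether or not it is serious under section 10.1.3; or*
- *3.* "If the DSMB recommends stopping due to a safety signal as described in section 10.4".

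No other threshold changes. Dropping the seriousness requirement from the whole list is not recommended. At an assumed 15% reaction rate (3 device-related events over 20 earlier subjects), that would pause roll-in with probability 1 − 0.85^10 = 80.3%.

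The cost is two lines of protocol text and matching DSMB charter wording, submitted as an amendment to FDA and the IRB. No new data collection is needed, since severe events already reach the sponsor within 5 working days. The downside is the extra chance of an early pause, at most 9.6% at a 1% severe-event rate and 40.1% at 5%. Each pause brings a DSMB investigation, a report to FDA and an agreed restart.

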10.1.6 Unanticipated Adverse Device Events

According to 21 CFR 812.3(s), a Unanticipated Adverse Device Event (UADE) is any serious adverse effect on health or safety or any life-threatening problem or death caused by, or associated with, a device, if that effect, problem, or death was not previously identified in nature, severity, or degree of incidence in the investigational plan or application (including a supplementary plan or application), or any other unanticipated serious problem associated with a device that relates to the rights, safety, or welfare of subjects.

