10.3 Adverse Event Reporting

All AEs and ADEs will be recorded by the investigator or designee on the case report forms (CRFs) provided. The investigator at each site is ultimately responsible for reporting AEs to the IRB according to IRB requirements and to the sponsor in accordance with the Investigational Plan and applicable FDA regulations. The site will be instructed to report all AEs considered moderate or severe and all local skin reactions to Candesant within 5 working days of the identification of the AE.

If an Adverse Event is considered a local skin reaction within the treated area, photos are required to be submitted as part of the Adverse Event Report. Submitted photos should show documentation of AE onset, AE progression and/or healing and AE

CANDESANT BIOMEDICAL	CLINICAL STUDY PROTOCOL SAHARA STUDY	Document #: CB-CLP-001 Revision: E
-------------------------	---	---------------------------------------

resolution (if applicable). Photos are to be taken with a high-resolution camera with the arm in the standardized treatment position and adequately illuminated. Photos are to be marked with Subject ID, date and subject side (i.e. Right or Left). Photos are to be taken with a measurement calibration reference visible.

AEs or complications meeting the definition for UADEs must be reported by the investigator to the sponsor as soon as possible, but in no event, later than 10 working days after the investigator first learns of the event. The sponsor will conduct an evaluation of any reported UADEs and will report the results of this evaluation to the FDA, IRBs, and participating investigators within 10 working days after first receiving notice of the event.

Descriptive and photographic data will be recorded and maintained on file for all AEs regardless of severity or device-relatedness. All observed local skin reactions will also be recorded.

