11.2 Potential Risks

The identified potential risks to the study subject that may be associated with treatment for excessive sweating or hyperhidrosis of the axilla are shown below. The risks of these events occurring for subjects treated during the Sahara Study have been mitigated as much as possible by device design and training

- Allergic reaction to device materials
- Blister formation
- Burning or stinging
- Decreased hair growth
- Discomfort / Pain
- Discomfort during post-treatment cleaning
- Infection
- Injury to eyes or mouth, if gloves or hands that handled the device touch
- Intolerance of deodorant
- Irritation
- Itching, tightness, tingling
- Numbness or altered sensation
- Redness (erythema), blotchiness, bumps
- Scar or contracture
- Skin corrosion
- Skin discoloration
- Skin erosion
- Sweating in other parts of the body
- Swelling (edema) or bruising
- Thermal Injury

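### After subject 10 the only automatic stopping trigger counts severity grade alone, so a serious device-related event graded moderate adds nothing to the 10%

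*Protocol*

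**What the plan says.** Protocol 11.5 has two sets of safety stopping rules.

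- **First 10 subjects.** The trigger is "One report of a Serious Adverse Event due to" any of a list of local causes, such as thermal or caustic injury, blister, erosion or infection. The test is seriousness.
- **After 10 subjects, item 1.** "If 10% of N-SWEAT treated subjects have a reported severe device-related Adverse Event as defined in Table 6". The test is the severity grade.
- **After 10 subjects, item 2.** "If the DSMB recommends stopping due to a safety signal as described in section 10.4". This depends on judgement.

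Seriousness and severity are separate scales. Section 10.1.3 defines a serious event by its consequence, including permanent impairment of a body structure. Section 10.1.4 defines a serious adverse device event as a device-related event with such a consequence and asks for no grade. Section 10.2.1 says that the grade does not determine seriousness, and the Table 6 footnote adds "Severe does not indicate an SAE (Serious Adverse Event".

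On the flow of information, Section 10.3 has sites "report all AEs considered moderate or severe and all local skin reactions to Candesant within 5 working days". Section 10.4 gives the DSMB three roles: to convene as needed on events related to stopping rules, "To conduct a monthly blinded review of all AEs reported during enrollment", and to request unblinding and investigate a safety signal. It leaves operating detail to a charter that is not in the file. The SAP contains no stopping rule. Its Section 10 uses DSMB-determined severity, but for the safety summaries.

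**The concern.** The rule for the first 10 subjects was built on seriousness. When the randomized cohort starts, the automatic rule switches to severity grade, and seriousness drops out of it.

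Table 6 separates moderate from severe mainly by how far an event disrupts daily life and how much treatment it needs. A permanent scar in the axilla could qualify as serious through permanent impairment without ever incapacitating the subject. If the investigator reports it as moderate, item 1 ignores it, however many such events there are.

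The expedited route for unanticipated adverse device events may not catch it either. That definition turns on an effect that "was not previously identified in nature, severity, or degree of incidence in the investigational plan", or on another unanticipated serious problem, and Section 11.2 already lists "Scar or contracture" and thermal injury among the potential risks.

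At stake is whether the one trigger that needs no judgement sees every serious injury from a device that, by Protocol 8.7.2, can cause alkaline or thermal burns.

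**Working it through.** **Plan's own figure.** The 10% level is stated without derivation, so there is nothing to reproduce. The check has two parts: what item 1 counts, and how much the omission changes its behaviour.

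**What is counted**

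| Event (device-related) | First-10 rule | After-10 item 1 |
|---|---|---|
| Serious, listed cause, graded severe | triggers | counts |
| Serious, listed cause, graded moderate | triggers | counts 0 |
| Not serious, graded severe | does not trigger | counts |

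**Inputs from the documents**
- 10 roll-in subjects on N-SWEAT (Protocol 9.5.1) and 55 randomized to it (9.3), so at most 65 treated.
- Item 1 is read as at least 10% of all N-SWEAT subjects treated so far, roll-in included.

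**Assumptions, not in the documents**
- Severe device-related rate p = 5%, with 2% and 10% as a range.
- Serious-but-moderate rate q = 0.2% to 1% in the randomized N-SWEAT subjects.
- Item 1 is checked after each N-SWEAT subject from the 11th to the 65th.
- The roll-in cohort either has severe events at rate p (random roll-in) or has none.

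**Threshold.** The number of subjects needed at n treated is ceil(0.10 × n): 2 at 11-20, 3 at 21-30, 4 at 31-40, 5 at 41-50, 6 at 51-60 and 7 at 61-65. One event cannot fire the rule alone, because 1/11 = 9.1%.

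**Method.** Exact sequential binomial: carry the distribution of the running count forward one subject at a time and, at each n, move to 'fired' all probability at or above the threshold. With serious-but-moderate events counted, each randomized N-SWEAT subject counts with probability 1 − (1 − p)(1 − q).

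**Item 1 as written:** random roll-in, 0.333 at p = 5% and 0.787 at p = 10%; none in roll-in, 0.154 and 0.571. These describe the existing rule, not the gap.

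**Effect of counting serious-but-moderate events, p = 5%**

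| q | Random roll-in | None in roll-in |
|---|---|---|
| not counted | 0.333 | 0.154 |
| 0.2% | 0.346 | 0.166 |
| 0.5% | 0.366 | 0.187 |
| 1% | 0.400 | 0.222 |

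Treating the two categories as mutually exclusive (rate p + q) changes these by at most 0.004; the largest values become 0.403 and 0.226.

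**Effect if exactly one such event occurs**, its position averaged over subjects 11 to 65 and all other subjects at rate p (not counted, then counted):

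| p | Random roll-in | None in roll-in |
|---|---|---|
| 2% | 0.065 to 0.129 | 0.020 to 0.061 |
| 5% | 0.326 to 0.450 | 0.148 to 0.268 |
| 10% | 0.779 to 0.863 | 0.556 to 0.707 |

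This second table is conditional on the event having happened. The chance of at least one among 55 randomized N-SWEAT subjects is 1 − (1 − q)^55, which is 10% at q = 0.2% and 42% at q = 1%.

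**The case against.** The strongest reply is that the category is nearly empty. The event must meet an outcome such as hospitalization or permanent impairment and yet be graded as a minor inconvenience that simple measures usually improve. Most serious axillary burns or infections would disrupt daily life or need systemic treatment, which is Table 6 severe. Appendix B calls its top erythema rating severe, and Appendix H refers third-degree and chemical burns to a burn center. No serious adverse events were reported in the two earlier studies (Protocol 3.3). All of this stands, and it is why the unconditional gains are modest.

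Other layers also act. The sponsor hears of moderate and severe events within 5 working days. Running safety reports go to FDA after randomized subjects 30, 60 and 90 (Protocol 6.1, SAP 7). The sponsor or investigator may discontinue the study under Section 15.1. Item 2 lets the DSMB stop for a safety signal of any grade. These layers reduce the consequence of the gap, but all rest on judgement. None puts the event into the automatic count.

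A strict roll-in rule followed by a rate rule is a defensible staged design. That also stands. The point concerns what the rate rule counts; neither the staging nor the 10% level is challenged.

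**Conclusion.** The point holds, in a narrow form. Item 1 omits serious device-related events graded moderate, although the protocol itself treats seriousness as a separate scale and built its first rule on it. At an assumed 5% severe rate and a 0.2% to 1% serious-but-moderate rate, the omission lowers the chance that item 1 fires by roughly 1 to 7 percentage points. If one such event occurs, it lowers that chance by about 12 points. The documents give neither rate. This is an inexpensive improvement to consider and does not show that the trial is unsafe as designed.

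A reader might infer more: that such an event would not reach the DSMB for up to a month while about 18 more subjects receive N-SWEAT (110 / 2 / 3 = 18.3 per month at planned accrual). The documents do not support that as a shown gap. They do not require earlier routing, but the charter that would set it is not in the file, and Section 10.4 lets the DSMB convene as needed. The 18 is also a worst case. The average wait is half a month, about 9 subjects, and most of them would be treated under the fix as well, since one event does not suspend the study.

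Nor do the documents support reading the after-10 rules as leaving serious events without any safeguard, or as needing suspension on a single event.

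**What to change.** Reword after-10 item 1 of Protocol 11.5 along these lines: *at least 10% of all N-SWEAT-treated subjects, roll-in and randomized together, have a device-related adverse event that is either severe (Table 6) or serious (Section 10.1.4)*. The roll-in words only confirm the plain reading, since Sections 6.1 and 9.5.3 already pool the two cohorts for safety.

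The cost is one sentence of protocol wording and a slightly higher chance of a temporary suspension for root cause review. The 10% level is unchanged and single-event suspension is not restored.

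Separately, confirm that the DSMB charter sends any serious adverse device event to the DSMB promptly, for example within 5 working days of sponsor receipt. If it does, nothing further is needed.
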